## EEG ANALYSIS

We will record the EEG data using Sedtrace (SedLine®) electrodes on the forehead located approximately at Fp1, Fp2, F7 and F8, the ground electrode at approximately Fpz and the reference electrode approximately 1 centimeter above Fpz. The data will be recorded with a preamplifier bandwidth of 0.5 to 92 Hz, a sample rate of 89 Hz, with a resolution of 16 bits and 29 nanovolts. Electrode impedance will be kept less than 5 kΩ on each channel.

For each patient, we will select 2-minute EEG segments that will represent the baseline period, the response to the propofol bolus (burst suppression, yes or no) and the phase of maintenance of general anesthesia prior to cardiopulmonary bypass. We will visually inspect the selected segments in both time and spectral domains to ensure data quality. We will calculate the multitaper spectral estimates using Matlab's Chronux toolbox with the following parameters: window length  $T = 2$  seconds without overlap, product of time bandwidth  $TW = 3$ , number of tapers  $K = 5$ . We will equally weight the signals from Fp1, Fp2, F7 and F8 channels. Patients will be considered to present burst suppression if they present alternating episodes of spontaneous high amplitude electrical activity (bursts) followed by suppression periods longer than 1 second (electrical variability  $<10 \mu\text{V}$ ). These analyzes will be performed in time domain as well as spectral domain.

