## STATISTICAL ANALYSIS

Initially, we will study the association between burst suppression (yes or no) with POD (yes or no) using univariate logistic regression. In addition, we will perform a univariate analysis for known risk factors for PDO (preoperative cognition, frailty, temperature in CPB, etc). Subsequently, we will perform a multivariate analysis with logistic regression to study the association between burst suppression with POD, after confounding variables adjustment. We will then use our data to generate a ROC curve and determine the area under the curve, sensitivity, specificity, positive predictive value, and negative predictive value of burst suppression to predict POD. Finally, we will use our variables to create a predictive model of POD that includes the burst suppression and other known risk factors for POD.

For descriptive statistics, continuous data will be presented using the mean  $\pm$  standard deviation or the median and its interquartile range, as appropriate. In addition, the groups will be compared by Student's t test for independent samples or the Mann-Whitney U test according to their distribution. In the case of categorical data, they will be presented as absolute counts and their corresponding percentage. Differences will be studied using Fisher's test or Chi square. For the association study, univariate and multivariate linear or logistic regressions will be performed, as appropriate. A significance level of 0.05 with its respective 95% confidence interval will be considered. All calculations will be performed in R statistical language.

Sample size calculation: With a sample of 72 subjects, we will have 80% power to detect a difference if the proportion of patients that present POD and burst suppression is 0.66 and the proportion patients that present POD and that do not present burst suppression is 0.33 with a significance level of 0.05 using a chi-square test. Considering 10% data loss, we will recruit a total of 80 patients.

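### Should the study have been sized for the confounder-adjusted regression rather than for the unadjusted chi-square test?

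*Combined protocol and SAP*

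**What the plan says.** All the relevant text is under STATISTICAL ANALYSIS, apart from the definition of the exposure.

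- Sizing: "With a sample of 72 subjects, we will have 80% power to detect a difference if the proportion of patients that present POD" takes its planning values, the first given as "the proportion of patients that present POD and burst suppression is 0.66", the second as 0.33 for patients without burst suppression, and the comparison made "with a significance level of 0.05 using a chi-square test".
- Recruitment: "Considering 10% data loss, we will recruit a total of 80 patients".
- Order of analyses: an unadjusted logistic regression of POD on burst suppression comes first. After univariate screening of "known risk factors for PDO (preoperative cognition, frailty, temperature in CPB, etc"), "we will perform a multivariate analysis with logistic regression to study the association between burst suppression with POD, after confounding variables adjustment". ROC measures and a prediction model follow.
- Reporting: the section sets a 0.05 significance level and commits to 95% confidence intervals.
- Exposure (EEG ANALYSIS): a classification of "the response to the propofol bolus (burst suppression, yes or no"). It is observed, not allocated.

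The plan gives no expected frequency of burst suppression, no final covariate list, no expected adjusted odds ratio and no power for the adjusted model. It does not say which association analysis is primary.

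**The concern.** Burst suppression is observed, so frailer or cognitively weaker patients may show it more often and may also develop delirium more often. The adjusted odds ratio is the result that separates burst suppression from those factors. Adjusting for such a confounder does two things: it removes part of the crude gap between 0.66 and 0.33, and it widens the standard error because exposure and confounder overlap.

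The sizing has almost no slack to absorb either effect. The unadjusted power is barely above 80%, and the extra eight recruits are already assigned to data loss. If the adjusted test has much less than 80% power, a non-significant adjusted result could be taken as evidence that burst suppression adds nothing to known risk factors, when the study was simply too small to show that it does.

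**Working it through.** **1. Inputs from the plan.** POD rates 0.66 and 0.33, significance level 0.05, N = 72, data loss 10%. Three assumptions are added: the rates apply within the two burst suppression groups (the reading that reproduces 72), the test is two-sided, and the split is equal (36/36).

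**2. The plan's own figure.** With mean rate 0.495, the pooled-variance formula gives

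n per group = [1.96·√(2·0.495·0.505) + 0.8416·√(0.66·0.34 + 0.33·0.67)]² / 0.33² = (1.386 + 0.562)² / 0.1089 ≈ 34.8, so 35 per group or 70 in all.

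At 36 per group, power = Φ[(0.33·√36 − 1.386)/0.667] = Φ(0.89) = 0.813. Exact enumeration of the uncorrected chi-square gives 0.804. Recruitment: 72/0.9 = 80. The figure reproduces.

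**3. Adjusted test, approximation.** The crude odds ratio is (0.66/0.34)/(0.33/0.67) = 3.94, with log 1.371. At 36/36, SE² = 1/(36·0.2244) + 1/(36·0.2211) = 0.249, so SE = 0.499. Let R² be the share of burst suppression variance explained by the covariates and a the proportional shrinkage of the log odds ratio:

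power = Φ[1.371·(1 − a)·√(1 − R²)/0.499 − 1.96].

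- a = 0, R² = 0: 0.784
- a = 0, R² = 0.10: 0.741
- a = 0.10, R² = 0.10: 0.650

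**4. Adjusted test, simulation.** N = 72, equal split, crude rates held at 0.66 and 0.33, one confounder plus two unrelated covariates, two-sided Wald test. The unadjusted power in the same data is 0.80 to 0.81 throughout. The last column is the proportion of simulated trials with a significant crude and a non-significant adjusted result.

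| R² | Confounder OR per SD | Adjusted OR implied | Adjusted power | Crude significant, adjusted not |
|---|---|---|---|---|
| 0 | 1.0 | 3.94 | 0.80 | – |
| 0 | 2.0 | 4.55 | 0.84 | – |
| 0.02 | 1.5 | 3.70 | 0.74 | 7% |
| 0.05 | 1.5 | 3.45 | 0.69 | 12% |
| 0.05 | 2.0 | 3.31 | 0.64 | 18% |
| 0.10 | 1.5 | 3.20 | 0.61 | 19% |
| 0.10 | 2.0 | 2.90 | 0.53 | 29% |

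Among trials with a significant crude result, the discordant pattern runs from 0.07/0.80 ≈ 9% to 0.29/0.80 ≈ 36%.

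**5. What drives the loss.** Holding the crude rates fixed makes the true adjusted odds ratio shrink as confounding grows, so much of the drop is lower power for a smaller effect. If the adjusted odds ratio is held at 3.94 instead (confounder OR 1.5), power at N = 72 is 0.77 at R² 0.05 and 0.74 at R² 0.10, against 0.80 with no confounding: a loss of about 3 to 6 points.

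**6. Where there is little or no loss.** At a confounder difference of 0.1 SD between groups, adjusted power is 0.80 at N = 72. At 0.2 SD with all 80 analysed it is 0.81 to 0.82. Prognostic covariates unrelated to burst suppression raise power (0.83 to 0.87 in the cases run), and in a case with negative confounding it is 0.88.

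**7. Split.** By the pooled formula, unadjusted power at N = 72 is 0.813 at 50% burst suppression, 0.798 at 40%, 0.746 at 30% and 0.634 at 20%. The documents do not indicate which applies.

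**The case for a change.** The best case for a change is that the adjusted odds ratio is what readers will use to judge whether burst suppression matters beyond frailty and cognition, that the plan itself calls the adjustment variables confounders, and that a sentence limiting the 80% to the unadjusted test would cost nothing. The facts behind this stand: the adjusted model has no stated power, neither analysis is labelled primary, the split is unstated, and moderate positive confounding would take adjusted power below 80%.

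Two parts do not carry through. A larger sample can be justified only by choosing a confounding strength. At a confounder OR of 1.5 per SD and an equal split, about 94 evaluable patients (94/0.9, so 105 recruited) are needed at R² 0.05 and about 113 (126 recruited) at R² 0.10. These show sensitivity to invented inputs and do not set a required size. The no-cost sentence would largely repeat what is there: the power statement already names the chi-square test, and results are already to be reported with 95% confidence intervals. The plan contains no rule that reads a non-significant adjusted result as absence of an independent association.

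**Conclusion.** No change is needed. Sizing a single observational cohort on its first-listed, unadjusted association is a fair choice, and 72 analysed with 80 recruited is correct for that test at roughly equal groups. The plan states no power for the adjusted model, so it misses no figure of its own.

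The shortfall in adjusted power is real but conditional. It ranges from nothing under weak or negative confounding to about 0.61 at R² 0.10 with a confounder OR of 1.5 per SD, and 0.53 with an OR of 2. All of these values rest on assumed confounding and an equal split. Discordant crude and adjusted results are a minority outcome in every case examined. Naming the primary analysis, its covariates and the expected split would make the plan easier to read but would alter no result. An analyst would report the adjusted odds ratio with its interval and judge its precision from that.
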